3.3.6.4 Procedures for handling incorrect enrolled patients

Patients not meeting the inclusion/exclusion criteria for the study should, under no circumstances, be enrolled into the study - there can be no exceptions to this rule.

Where patients not meeting the study criteria are enrolled in error, or where patients subsequently fail to meet the criteria for the study post enrolment, the investigator will in conjunction with AstraZeneca discuss whether such a patient should withdraw from study taking into consideration ethical and safety factors and the discussion and rationale for each decision will be documented.

Incorrectly enrolled subjects will be listed, and only included in analysis if subjects' data were used for dose escalation decision.

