6.2 Description of outcome variables in relation to objectives and hypotheses

The primary objective of this study is to assess the safety and tolerability of AZD8330 in patients with advanced malignancies. This objective will be assessed by AEs, clinical chemistry, haematology, urinalysis, vital signs, MUGA scan/Echocardiogram, ECGs Ophthalmologic examination, and O₂ saturation.

The secondary objective of determining the pharmacokinetics of AZD8330 and any known major metabolites following both single and multiple oral dosing of AZD8330 in patients with advanced malignancies will be assessed by derivation of pharmacokinetic parameters for both AZD8330 and any known major metabolites, which may include include C_{max}, t_{max}, AUC, CL/F, and t_{1/2}.

The secondary objective of investigating the extent of pERK inhibition in PBMCs, will be assessed by the change in pERK in PBMCs at 30 minutes, 1 hour 30 minutes, 4, 8 and 24 hours post-dose compared to pre-dose levels.

If the data are suitable, potential relationships between plasma AZD8330 and any known major metabolites concentrations/exposure and changes in safety parameters will be investigated using a graphical approach and/or appropriate PK/pharmacodynamic modelling techniques.

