6.3 Description of analysis sets

Population	Definition
Evaluable for safety	This will include all patients who received at least one dose of study medication ^a .
Evaluable for PK analysis	This is a subset of the safety population that includes all patients who provide AZD8330 concentration data and/or any known major metabolites concentration-time data.
Evaluable for Dose Escalation Evaluation (Part A)	This is a subset of the safety population that includes all Part A patients who have had all PK assessments (Day 1) performed, and who have sufficient safety evaluations performed during 35 days dose period from first dose at the discretion of the Safety Review Committee, or have suffered a DLT.

a If a patient discontinues study medication and starts another anti-cancer therapy, all data after 30-day follow-up period for that patient will be excluded from the assessment of safety.

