6.4.1 Safety Data

Safety data will not be formally analysed. All patients who receive at least one dose of AZD8330 will be included in the assessment of AE profile (evaluable for safety population). Other safety data will be assessed in terms of clinical chemistry, haematology, urinalysis, vital signs, MUGA scan/Echocardiogram, ECGs, ophthalmologic examination, and O₂ saturation. At the end of the study, appropriate summaries of all safety data will be produced, as defined below and in the SAP.

Data from all cycles of initially randomised treatment will be combined in the presentation of safety data. AEs will be listed individually by patient and dose group. For patients who have a dose modification, all AEs (due to drug or otherwise) will be assigned to the initial dose

group. The number of patients experiencing each AE will be summarised MedDRA system organ class (SOC), MedDRA preferred term (PT) and CTC grade. The number and % of patients with adverse events in different categories (e.g. causally related, CTC grade ≥ 3 etc) will be summarised by dose group, and events in each category will be further summarised by MedDRA SOC and PT, by dose group.

Any AE occurring before treatment (ie, before study Day 1) will be included in the data listings but will not be included in the summary tables of adverse events. In addition, a separate data listing of pre-treatment AEs will be produced.

Any AE occurring within 30 days of treatment withdrawal will be included in the AE summaries. Any events in this period that occur after a patient has received further therapy for cancer (following withdrawal of study medication) will be flagged in the data listings. AEs occurring more than 30 days after withdrawal of study medication will be listed separately, but not included in the summaries.

Clinical chemistry, haematology, urinalysis, vital signs, MUGA scan/Echocardiogram, ECGs, ophthalmologic examination, and O₂ saturations will be listed individually by patient and dose group and summarised by treatment dose, as follows:

Haematology, clinical chemistry, vital signs and ECG data will be suitably summarised by dose level for all patients by:

- summary statistics of observed values: mean, standard deviation, minimum, maximum, n
- summary statistics of change from baseline values: mean, standard deviation, minimum, maximum, n

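### The rule in Section 3.3.6.4 for incorrectly enrolled patients contradicts the all-dosed safety set in Sections 6.3 and 6.4.1, and following it would drop some dosed patients from the primary safety summaries

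*Protocol*

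**What the plan says.** Section 3.3.6.4 deals with patients who are found not to meet the entry criteria, whether enrolled in error or failing the criteria later. Withdrawal is discussed case by case. On analysis the section says: "Incorrectly enrolled subjects will be listed, and only included in analysis if" their data contributed to a dose escalation decision. It names no particular analysis and makes no exception for safety.

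Section 6.3 defines the set evaluable for safety: "This will include all patients who received at least one dose of study medication". Its one footnote concerns data collected after the 30-day follow-up in patients who start another anti-cancer therapy; it says nothing on eligibility. Section 6.4.1 repeats the rule: "All patients who receive at least one dose of AZD8330 will be included in the assessment of AE profile".

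Section 6.2 confirms what these summaries are for: "The primary objective of this study is to assess the safety and tolerability of AZD8330".

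Section 6.3 also defines a narrower set for dose escalation: "This is a subset of the safety population that includes all Part A patients who have had all PK assessments (Day 1) performed". Those patients must in addition have enough safety evaluation over 35 days, as judged by the Safety Review Committee. A patient with a DLT also qualifies.

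**The concern.** For a patient who took AZD8330, proved ineligible and did not contribute to a dose decision, one section says leave out and two say include. A programmer cannot obey all three.

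Safety and tolerability is the primary objective, and the dose groups are small. If 3.3.6.4 were followed, some treated patients' findings would be missing from both numerator and denominator of the safety tables. Membership of the primary summaries would also turn on whether a patient's data were used in a meeting held after dosing. That is partly a matter of committee judgement and is not fixed in advance.

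**Working it through.** The protocol gives no figure to reproduce. The check is a comparison of the rules, followed by simple proportions.

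**Step 1. Apply both rules to each type of incorrectly enrolled patient.**

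| Patient | Section 3.3.6.4 | Sections 6.3 and 6.4.1 |
|---|---|---|
| Never dosed | Listed, not analysed | Not in safety set |
| Dosed, data used for a dose decision | Analysed | In safety set |
| Dosed, data not used for a dose decision | Listed, not analysed | In safety set |

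Only the third row conflicts. The sentence in 3.3.6.4 cannot be confined to undosed patients, because its exception covers people whose data informed escalation, and they must have been dosed.

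**Step 2. Can the third row occur?** The dose-escalation set in 6.3 is by definition smaller than the safety set. Routes out of it include incomplete Day 1 PK sampling, or early withdrawal without a DLT once ineligibility is found. Under 3.1.4.1 the committee meets as soon as possible after six patients complete 35 days, so patients seven to nine in a cohort may have little data by then. Section 5.2 says decisions rest on unvalidated data, so ineligibility may emerge only later.

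**Step 3. Which findings are at risk?** Under 3.1.4.2, a treatment-related non-haematological Grade 3 or 4 toxicity in the first 35 days, despite supportive care and not clearly due to the disease, is a DLT. A DLT makes the patient evaluable under 6.3, so such a patient would normally be kept. What could be lost is lower-grade events, events judged unrelated, events after Day 35, haematological Grade 3 events that are not DLTs, and laboratory, ECG, MUGA/echocardiogram and eye results. Section 4.1 lists all of these among the primary variables.

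**Step 4. Size per patient.** Cohorts have n = 6 to 9 (Section 3.1.1). One patient's share is 1/n: 1/6 = 16.7% and 1/9 = 11.1%.

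Let x of n dosed patients have a given event, and let one dosed patient be dropped. The rate x/n becomes (x − 1)/(n − 1) if that patient had the event, and x/(n − 1) if not.

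| All dosed (6.3) | Dropped patient had the event | Dropped patient did not |
|---|---|---|
| 1/6 = 16.7% | 0/5 = 0.0% | 1/5 = 20.0% |
| 2/6 = 33.3% | 1/5 = 20.0% | 2/5 = 40.0% |
| 2/9 = 22.2% | 1/8 = 12.5% | 2/8 = 25.0% |
| 3/9 = 33.3% | 2/8 = 25.0% | 3/8 = 37.5% |

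These rows assume one affected patient in the cohort. The protocol does not say how many to expect.

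**Step 5. Other sets.** The PK set in 6.3 takes all safety patients who provide concentration data. The tumour-response summaries in 6.4.3.2 take all safety patients with a baseline and at least one follow-up RECIST assessment. Neither has an eligibility exclusion, so 3.3.6.4 conflicts with these as well.

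**The case against.** The best defence is that few patients would be affected. Section 3.3.6.4 does not cite the dose-escalation set in 6.3. Section 3.1.4.1 has the committee review available clinical data and consider all clinical findings in the completed cohort, so on a broad reading nearly every dosed patient's data are used. Section 3.5 requires eligibility to be established before a patient number is assigned, so some incorrectly enrolled patients will never be dosed. This argument stands as a limit on size. It does not settle which rule governs, and the breadth of the word used is itself undefined.

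A reader might infer that ineligible patients are kept only when they have a DLT, so that selection follows outcome outright. The text does not support that. Section 3.3.6.4 keeps anyone whose data were used, and under 6.3 a patient with full Day 1 PK and sufficient 35-day safety evaluation is evaluable without a DLT. Selection related to outcome could arise only among patients who fall short of those requirements.

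A reader might also infer that these patients' toxicity disappears from the report. It does not: 3.3.6.4 keeps them listed, 6.4.1 lists adverse events by patient, and serious events are reported under 4.5.1.3 whatever the patient's eligibility. Only the summaries are exposed.

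Finally, the question cannot simply be left to a separate analysis plan. Section 6.1 says none will be prepared, although 6.4.1 mentions one. In either case the conflict is between two rules the protocol already states.

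**Conclusion.** The contradiction is real and should be corrected. Followed as written, 3.3.6.4 takes dosed, ineligible patients out of the primary safety summaries when their data did not inform a dose decision, while 6.3 and 6.4.1 keep them in.

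Each such patient is 11% to 17% of a dose group, enough to move a descriptive rate noticeably in either direction. The total effect is unknown because the number of such patients is not given, and it may be small.

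A reader might go further and infer that the MTD is in doubt. It is not: it rests on committee decisions, and patients used for those decisions are retained under either rule. There is also no formal hypothesis test (6.4) for the conflict to distort. What is undefined is the denominator of the descriptive safety tables, with inclusion depending partly on judgement exercised after dosing.

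**What to change.** Replace the analysis sentence in 3.3.6.4 with: *Incorrectly enrolled patients who received at least one dose are included in the safety analysis set and flagged in the listings.* Sections 6.3 and 6.4.1 then need no change for safety.

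If the sponsor wants to exclude ineligible patients from the PK or tumour-response summaries, the definitions in 6.3 and 6.4.3.2 must be amended to say so. Otherwise those sets stand as defined and include them.

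The safety correction costs one sentence. It needs no new data and leaves the dosing and escalation rules untouched. Optional PK or response exclusions would add a wording change to each definition.

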3.3.6.5 Procedures for discontinuation from host genetic aspects of the study

Patients who discontinue from the study should always be asked specifically whether they are withdrawing or continuing their consent for this host genetic research. It must be established whether the patient:

- Agrees to the genetic sample and any DNA extracted from the sample being kept for host genetic research in the future.
- Withdraws consent for the sample to be kept for host genetic research in the future and wishes the sample to be destroyed. Destruction of the sample (or the DNA extracted from the sample) will only be possible so long as the particular sample is traceable. In the event that host genetic research has already been performed, AstraZeneca will retain the results and associated data for regulatory reasons but these will not be used in any subsequent analyses.

The principal investigator is responsible for providing written notification to AstraZeneca of any patient who has withdrawn consent for the use of the sample taken for host genetic research. AstraZeneca will provide written confirmation to the investigator of the actions taken with the sample, which must be filed in the investigator study file.

3.4 Treatments

3.4.1 Identity of investigational product and comparators

AstraZeneca Investigational Products section will supply AZD8330 open labelled clinical study material.

Table 2 Identity of investigational product

Investigational product	Formulation	Dosage form and strength	Manufacturer	Formulation number^a
AZD8330	Film Coated Tablets	0.5 mg	AstraZeneca	F013509
AZD8330	Film Coated Tablets	0.75 mg	AstraZeneca	F013526
AZD8330	Film Coated Tablets	1.5 mg	AstraZeneca	F013511
AZD8330	Film Coated Tablets	5.0 mg	AstraZeneca	F013513

^a Batch numbers for all investigational products will be identified in the clinical study report

3.4.2 Doses and treatment regimens

3.4.2.1 Tablets

AZD8330 tablet formulation drug product will be supplied in 0.5 mg, 0.75 mg, 1.5 mg and 5 mg strengths in high-density polyethylene (HDPE) bottles, each bottle will contain sufficient tablets for each patient treatment period, as appropriate. The Safety Review Committee will give dose recommendations, and patients will be required to take the same combination of tablet strengths to make up the relevant dose, as directed by AstraZeneca.

If patients are not able to tolerate AZD8330, dose reductions are permitted as described in Section 3.1.4.1. This will depend on doses available and doses selected for the oral formulation.

3.4.2.2 Part A (Dose Escalation Phase)

The first cohort will receive a single 0.5 mg dose of AZD8330 on Day 1, followed by 0.5 mg once daily (OD) continuous dosing from Day 8 onwards. Subsequent cohorts will be dispensed investigational product according to the dose directed by the Safety Review Committee (see Section 3.1.4.1). Each dose should be taken with approximately 240 ml (8 fl oz) water, and on an empty stomach no food or drink other than water for 2 hours prior to dosing and 1 hour after dosing (see Section 3.3.5).

3.4.2.3 Part B (Safety Expansion Phase) (Not applicable)

No longer applicable.

3.4.3 Labelling

Each bottle of AZD8330 Tablets 0.5 mg, 0.75 mg, 1.5 mg and 5 mg will be labelled by Investigational Products (IPS), AstraZeneca, or CRO.

Each bottle of AZD8330 will have a label permanently affixed to the outside and will be labelled in accordance with Good Manufacturing Practice and local regulations, stating that the material is for clinical trial / investigational use only and should be kept out of reach of

children. Labels will include blank lines for the patient enrolment code (E-code) and date dispensed.

3.4.4 Storage

All investigational products must be kept in a secure place under appropriate storage conditions. Descriptions of the appropriate storage conditions are specified on the investigational products label. The tablets should all be stored in their original packaging until use.

3.4.5 Accountability

It is the Investigator/institution's responsibility to establish a system for handling study treatments, including investigational products, so as to ensure that:

- deliveries of such products from AstraZeneca are correctly received by a responsible person (eg, a pharmacist)
- deliveries are recorded
- study treatments are handled and stored safely and properly
- study treatments are dispensed only to study patients in accordance with the protocol
- patients return all unused medication and empty containers to the Investigator.

At the end of the study, it must be possible to reconcile delivery records with records of usage and destroyed/returned stock. Records of usage should include the identification of the person to whom the study treatment was dispensed, the quantity and date of dispensing, and unused study treatment returned to the Investigator. Certificates of delivery and return must be signed, preferably by the Investigator or a pharmacist, and copies retained in the Investigator File.

All unused or returned medication, after drug accountability, should be destroyed at site wherever possible. In the event that this is not possible the medication should be returned to the local distribution centre for destruction.

3.5 Method of assigning patients to treatment groups

Written informed consent will be obtained before enrolment, when patients will be identified with a unique 7-digit enrolment number (E00NNXXX: NN being the centre number, XXX being the patient enrolment number at the centre.). Enrolment numbers will start at 999 in each centre and go down (eg, at centre 1, patients will be assigned e-codes E0001999, E0001998, E0001997, etc and E0002999, E0002998, E0002997, etc in centre 02).

Part A (Dose Escalation Phase)

Patient eligibility will be established before assigning a study patient number starting with number 101 in Part A. Patient numbers will be assigned strictly sequentially, by a central co-ordinator at AstraZeneca as patients are confirmed as eligible to receive treatment. If a patient discontinues from the study, the patient number will not be reused, and the patient will not be allowed to re-enter the study.

Replacement patients may enrol until the minimum required number of evaluable patients is available for assessment. Reasons for patient withdrawal will be given due consideration when enrolling patients.

3.6 Pre-study, concomitant and post-study treatment(s)

The following treatment/drugs are restricted in this study;

- No other chemotherapeutic agents, or investigational drugs should be administered whilst patients are receiving study medication.
- Any radiotherapy, biological or chemotherapy within 21 days prior to starting the study (not including palliative radiotherapy at focal sites).
- Recent major surgery within 4 weeks prior to entry into the study (excluding the placement of vascular access) which would prevent administration of study treatment.
- Patients who are receiving concomitant medications that are substrates for CYP450s 3A4, 1A2 and 2C9 should monitor for clinical signs of reduced efficacy of these agents (<http://medicine.iupui.edu/flockhart/table.htm>). In particular, patients who are on anticoagulant therapy (eg, warfarin) should have their anticoagulation tested more frequently when receiving AZD8330.
- Concomitant medications that are known inhibitors/inducers of CYP2C9 and 2C219 pathways (<http://medicine.iupui.edu/flockhart/table.htm>) should be recorded (dose, frequency and dates of dosing) in order to aid the pharmacokinetic interpretation of AZD8330 data.

Other medication that is considered necessary for the subject's safety and well-being may be given at the discretion of the investigator(s). The administration of all medication (including investigational products) must be recorded in the appropriate sections of the pCRF.

It is advisable that during the PK sampling periods of Part A, patients should avoid changes to or the addition of all concomitant medications, in particular any that are likely to affect the metabolism of AZD6244 (eg, CYP1A2 or 3A4 inducers), unless considered clinically essential for management of concurrent conditions.

3.7 Treatment compliance

Administration of study drug will be captured in the pCRF.

Study treatments are only dispensed to patients in accordance with the protocol. Patients must return all unused medication and packaging. At the end of the study, it must be possible to reconcile delivery records with records of usage and returned stocks. Any discrepancies must be accounted for. Certificates of delivery and return must be signed, preferably by the Investigator or a pharmacist.

4. MEASUREMENTS OF STUDY VARIABLES AND DEFINITIONS OF OUTCOME VARIABLES

4.1 Primary variable

The primary variables are incidence and severity of adverse events, clinical chemistry, haematology and urinalysis, vital signs, MUGA/Echo parameters, ECG parameters, ophthalmologic examinations and O₂ saturation.

4.2 Screening and demographic measurements

Prior to enrolment in the study, each patient will undergo an enrolment examination within 2 weeks prior to visit 2 (Day 1). This will consist of:

- Provision of written informed consent
- Evaluation against inclusion and exclusion criteria
- Recording of demographic data – date of birth, sex, height, weight, race
- Standard medical and surgical history and a physical examination.
- Smoking status
- Resting supine blood pressure (BP) and pulse measurement
- Pulse oximetry
- Full ophthalmological exam
- WHO performance status
- ECG
- Blood sample for standard clinical chemistry (including BNP), coagulation, and haematology assessments

- Urine sample for urinalysis
- MUGA Scan or echocardiogram
- Chest x-ray
- Pregnancy test (urine or serum) for female pre menopausal patients
- Baseline tumour assessment according to the Response Evaluation Criteria In Tumours' (RECIST) criteria (see [Appendix C](#)) in RECIST evaluable tumours within 4 weeks of dosing.
- Recording of any concomitant medications.

4.3 Pharmacokinetic measurements and variables

The methods for collection of biological samples and derivation of PK parameters are presented below and in the Laboratory Handbook for Investigators.

Depending on emerging data, the actual timings of these samples may change, but the total blood volume will not change. In order to fully elucidate the terminal elimination phase following a single dose of AZD8330 on Day 1 in Part A, if warranted by the data PK sampling may be redistributed to cover a 48 or 72h period (ie total number of samples will not change). If this occurs, dosing on these subsequent days (ie Days 2 and possibly 3) should be withheld.

Part A: Pharmacokinetic sampling

Blood samples for the determination of plasma AZD8330 will be taken on Days 1 and 15 as described below:

- Day 1: Pre-dose, 15 and 30 minutes and 1, 1 hour 30 minutes, 2, 4, 6, 8,12 (pre-dose 2nd dosing) and 24 hours post dose.
- Day 15: Pre-dose, 15 and 30 minutes and 1, 1 hour 30 minutes, 2, 4, 6, 8,12 (pre-dose 2nd dosing) and 24 hours post-dose (pre-dose Day 16 dose).
- Five sparse sampling on two additional days at steady-state, Days 22 and 29: pre-dose, 0.5, 1, 2 and 4 hours post-dose.

In addition to AZD8330, other major metabolites may be analysed from the same blood and urine samples if warranted and if a bioanalytical assay is available.

